4.3 EXCLUSION CRITERIA

1. Consumption of >3 units of alcohol per day (>21 units per week) if male and >2 units of alcohol per day (>14 units per week) if female for at least 3 consecutive months in the last 5 years (Note: 1 unit = 12 ounces of beer, 4 ounces of wine or 1 ounce of spirits/hard liquor).
2. History or presence of other concomitant liver diseases including:
 - Hepatitis B or C virus (HCV, HBV) infection
 - Primary sclerosing cholangitis (PSC)
 - Alcoholic liver disease
 - Definite autoimmune liver disease or overlap syndrome
 - Non-alcoholic steatohepatitis (NASH)
3. Cirrhosis with complications, including history or presence of: spontaneous bacterial peritonitis, hepatocellular carcinoma, bilirubin $> 2 \times$ ULN, ascites, encephalopathy, known esophageal varices or history of variceal bleeding and active or history of hepatorenal syndrome.
4. History of any venous thromboembolism, TIA, intracranial hemorrhage, neoplasm, arteriovenous malformation, vasculitis, bleeding disorder, coagulation disorders or screening blood tests that indicate altered coagulability (e.g. platelet count, aPTT, PTT or TT tests).
5. Patients with INR $>$ ULN at visit 1.

6. Patients with total bilirubin > ULN at visit 1 that is not due to Gilbert's syndrome.
7. Patients with >30% increase in ALT, total bilirubin, or INR between Visit 1 to Visit 2, unless both results (visit 1 and visit 2) are within the reference range.
8. Patients with serum creatinine >ULN according to the gender at Visit 1.
9. Patients with abnormal total creatine kinase (CK) OR lipase OR amylase at Visit 1.
10. Unstable cardiovascular disease, including:
 - unstable angina, (i.e., new or worsening symptoms of coronary heart disease within the past 3 months), acute coronary syndrome within the past 6 months, acute myocardial infarction in the past 3 months or heart failure of New York Heart Association class (III – IV) or worsening congestive heart failure, or coronary artery intervention, within the past 6 months
 - history of (within prior 3 months) or current unstable cardiac dysrhythmias
 - uncontrolled hypertension (systolic blood pressure [BP] >160 mmHg and/or diastolic BP >100 mmHg)
 - stroke or transient ischemic attack within the prior 6 months
11. History of malignancy in the past 5 years and/or active neoplasm with the exception of resolved superficial nonmelanoma skin cancer.

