4.4.1 Discontinuation of Subject Investigational Product (IP)

Patients with worsening liver function will not be enrolled in the study. Evidence of worsening liver function will be assessed based on the 2 initial laboratory values used to establish the baseline.

Elevations in ALT and/or AST, occurring after the initiation of study drug, that meet the definition of a potential Case of Drug-Induced Liver Injury per below;

1. If patients with abnormal baseline liver indices develop elevations of AST or ALT greater than 2x baseline or total bilirubin greater than 1.5x baseline values while on study, testing shall be repeated within 48 -72 hours.
2. If there are persistent elevations in ALT or AST greater than 2x baseline or TBL greater than 1.5x baseline values, then close observation (testing and physical examination 2-3 times per week) shall be initiated or study drug will be discontinued
- A decision to discontinue or temporarily interrupt the study drug will be considered based on factors that include how much higher baseline ALT and AST were relative to the upper limit of normal (ULN) and how much the on study ALT and AST levels have increased relative to baseline, in addition to

whether there is concomitant elevation of bilirubin or INR. Study drug will be discontinued or temporarily interrupted:

- a. When the baseline values were < 2x ULN, discontinue if ALT or AST increases to > 5x baseline,
- b. When the baseline values were \geq 2x ULN but < 5x ULN, discontinue if ALT or AST increases to >3x baseline,
- c. When the baseline values were \geq 5x ULN, discontinue if ALT or AST increases to > 2x baseline,
- d. Discontinue if ALT or AST increase > 2x baseline AND the increase is accompanied by a concomitant TBL increase to >2x baseline OR the INR concomitantly increases by >0.2,
- e. In any patients with signs and symptoms of fatigue, nausea, vomiting, right upper quadrant pain or tenderness, fever, rash, and/or eosinophilia (> 5%).

- If a patient lives in a remote area, laboratory testing can be performed locally and the results shall be promptly communicated to the investigator site promptly.
- If patient develops an adverse event of grade 3 that is probably or possibly related to study drug and any patient regardless of attribution to drug who develops a grade 4 or higher Common Terminology Criteria for Adverse Event (CTCAE version 4.03).

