- Parameters of renal function: IP is to be discontinued if the estimated glomerular filtration rate (eGFR) falls to <60 mL/min/1.73m² (calculated using Chronic Kidney Disease Epidemiology Collaboration (CKD-EPI) equation) and where the value is reconfirmed after 24 hrs repeat. Additionally, any subject who requires renal replacement therapy will also have IP discontinued.
- Patient will be immediately discontinued from study drug and followed until resolution of adverse event and laboratory values have returned to baseline, if any of the following criteria occur.

- a. TB \geq 3.0 mg/dL in individuals with normal baseline TB. In individuals with elevated baseline TB due to known Gilbert's syndrome, doubling of direct bilirubin will prompt immediate discontinuation of the study drug.
- b. Total CK $>$ 5x ULN
- c. Amylase and lipase $>$ ULN
- d. Hemoglobin $<$ 100 g/L or HCT $<$ 30%
- e. Platelets $<$ 100000/ μ L
- f. WBC $<$ 3.5 X 10⁹/L
- g. If more than 3 patients develop a CTCAE grade 3 or higher in the same category, or if 3 or more patients meet the above individual criteria (a to f) the trial may be stopped and/or unblended safety data will be evaluated.

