7 INVESTIGATIONAL PLAN

7.1 STUDY DESIGN AND PLAN

This is a Phase 2 prospective, multicentre, randomized, double-blind, placebo-controlled study includes a total 36 patients with a diagnosis of Primary Biliary Cholangitis. The study will be conducted over a period of up to 26 weeks and will include a 6-week Screening Phase, a 16-week Treatment Phase and a safety follow-up visit after 4 weeks.

Screening Phase:

- Visit 1 (Day -42): Patient eligibility for participation in the study will be assessed. Medical history will be obtained and physical examination, electrocardiogram (ECG) and laboratory evaluations (including serology, [anti-nuclear antibody, smooth muscle antibody and serum immunoglobulin level G], clinical chemistry, hematology, liver biochemistries, and urinalysis) will be performed. In patients with ANA or SMA antibody positive titers, a liver biopsy must have been performed to rule out autoimmune hepatitis or overlap syndrome. Female patients will undergo a pregnancy test. Serum ALP must be ≥ 1.67 upper limit of normal (ULN) to proceed further in the study.
- Visit 2 (Day -14 to -7): Liver biochemistries (ALT, ALP, total bilirubin (TB) and INR will be re-measured approximately 4 weeks from Day -42 to determine eligibility. Elevated ALP must be ≥ 1.67 ULN on 2 occasions in the Screening Phase and is necessary for study entry. If there is an increase of more than 30% in the levels of ALT, total bilirubin or INR at Day (-14) to Day (-7) [Visit 2] as compared to the values on Day (-42) [Visit 1], then such patients will not be eligible for study entry. The average of two assessments (Visit 1 and Visit 2) of liver biochemistries and INR will be considered as baseline values for these parameters.

Randomization & Treatment Phase:

- Visit 3: The Randomization & Treatment Phase will include 6 outpatient visits over a period of 16 weeks, including the randomization visit. Patients will be randomly assigned to receive either Saroglitzaz magnesium (2 mg or 4 mg) or placebo orally

once daily in addition to their ongoing treatment with UDCA (Patients unable to tolerate UDCA will receive only the investigational medicinal products), starting on Day 1 and continuing for 16 weeks. Efficacy and safety parameters will be assessed during each study visit as per the Schedule Visit Table 1.

- Visit 3.1: Patient will visit study site at 2 weeks after randomization visit for LFTs. The LFTs will be performed at local laboratory.

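### The immediate-stop rule for bilirubin (protocol 4.4.1, item a) omits a non-Gilbert patient whose averaged baseline is slightly above ULN

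*Protocol*

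**What the plan says.** Section 4.4.1 of the protocol has two lettered lists: one for ALT and AST elevations (a to e), and one of criteria for immediate discontinuation (a to g). Item a of the second list has two limbs. The first is TB at or above "3.0 mg/dL in individuals with normal baseline TB". The second reads: "In individuals with elevated baseline TB due to known Gilbert's syndrome, doubling of direct bilirubin will prompt immediate discontinuation of the study drug". The synopsis carries the same text.

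Three other rules decide who can be enrolled and what baseline means:

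- Exclusion 6 (4.3) removes "Patients with total bilirubin > ULN at visit 1 that is not due to Gilbert's syndrome". It sets no such cap at Visit 2.
- Exclusion 7 (4.3) removes "Patients with >30% increase in ALT, total bilirubin, or INR between Visit 1 to Visit 2", unless both values are in the reference range.
- Section 7.1 states: "The average of two assessments (Visit 1 and Visit 2) of liver biochemistries and INR will be considered as baseline values". SAP section 5 uses the same definition.

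Separately, 4.4.1 requires a repeat test within 48 to 72 hours if TB exceeds 1.5 x baseline in a patient with abnormal baseline liver indices. If the rise persists, "close observation (testing and physical examination 2-3 times per week) shall be initiated or study drug will be discontinued".

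**The concern.** The two limbs of item a would cover everyone if exclusion 6 guaranteed a normal baseline in every non-Gilbert patient. It does not, because baseline also includes a Visit 2 value that may lie above ULN. A non-Gilbert patient can therefore enter with a raised averaged baseline and fall under neither limb.

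At stake is an automatic hepatic stop in a liver-disease trial. Two patients without Gilbert's syndrome, one slightly below ULN at baseline and one slightly above, could both reach 3.0 mg/dL. The first must stop immediately; for the second the protocol leaves the decision to judgement. The second also cannot count through item a towards item g, under which three or more patients meeting the individual criteria may lead to the trial being stopped or to unblinded safety review.

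**Working it through.** **1. Largest possible baseline.** Write V1 and V2 for TB at Visits 1 and 2, in multiples of ULN, for a patient without Gilbert's syndrome.

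- Exclusion 6: V1 ≤ 1.00.
- Exclusion 7: V2 ≤ 1.30 x V1 whenever V2 is above ULN. The exception needs both values in range, so it cannot give an average above ULN.
- Baseline = (V1 + V2)/2, so the maximum is (1.00 + 1.30)/2 = 1.15 x ULN.
- An average above ULN requires (V1 + 1.30 x V1)/2 > 1, that is V1 > 2/2.30 = 0.87 x ULN.

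**2. Example.** V1 = 0.93 and V2 = 1.15. The rise is 1.15/0.93 = 1.237, or 24%, so the patient is eligible. Baseline is (0.93 + 1.15)/2 = 1.04 x ULN, which is neither normal nor due to Gilbert's syndrome.

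**3. Do other rules restore the mandatory immediate stop?** The protocol text available gives no ULN for TB, so assume 1.0 to 1.3 mg/dL. For baselines from 1.00 to 1.15 x ULN:

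- The 1.5 x baseline trigger lies between 1.5 x 1.00 x 1.0 = 1.50 mg/dL and 1.5 x 1.15 x 1.3 = 2.24 mg/dL. It fires before or at 3.0 mg/dL, but a persistent rise leads to close observation or a stop.
- 3.0 mg/dL is between 3.0/(1.15 x 1.3) = 2.01 and 3.0/(1.00 x 1.0) = 3.00 x baseline. The bilirubin part of item d in the ALT/AST list (above 2 x baseline) is therefore met, but item d also needs ALT or AST above 2 x baseline.
- Item e of that list needs symptoms or eosinophilia, and allows a temporary interruption.
- The CTCAE rule depends on grade, and at grade 3 on attribution. It is outside the immediate-stop list, and the documents do not print the grade limits.

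A rise that is isolated (ALT and AST not above 2 x baseline, no item e findings, no CTCAE rule met) has no mandatory stop.

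**4. How many patients.** The documents give no bilirubin distribution. The following are assumptions: lognormal TB, between-patient log-SD 0.30 or 0.45, within-patient CV 10% to 30%, and 1.5 million simulated patients per setting. The share is the fraction of eligible patients with an averaged baseline above ULN.

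| Assumed median TB (x ULN) | Share of eligible | Expected of 36 |
|---|---|---|
| 0.40 | 0.03% to 0.25% | 0.01 to 0.09 |
| 0.50 | 0.20% to 0.63% | 0.07 to 0.23 |
| 0.60 | 0.67% to 1.20% | 0.24 to 0.43 |
| 0.70 | 1.33% to 1.88% | 0.48 to 0.68 |
| 0.85 | 2.22% to 3.75% | 0.80 to 1.35 |

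Overall this is 0.01 to 1.35 of 36, or 1.35 x 24/36 = 0.90 at most among the 24 on active drug.

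**The case against.** The strongest reply is that this patient is well watched and that the intent is plain. The repeat-test rule is written for patients with abnormal baseline indices, and it acts at or below about 2.24 mg/dL under the assumed ULN. A stop is expressly available, the investigator may withdraw a patient in that patient's interest (4.4), and the Data Monitoring Committee reviews bilirubin elevations (7.6). Item a also appears to name the same two groups that exclusion 6 admits, so most sites would probably apply 3.0 mg/dL to a patient just above ULN. All of this stands, and it is why the point is minor. It does not supply the automatic stop, which is meant not to depend on judgement.

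A second reply is that 4.4.1 already says "Patients with worsening liver function will not be enrolled in the study", judged on the two baseline values. Every patient in the gap has moved from at or below ULN to above it during screening, so an investigator could call that worsening. But the sentence sets no threshold, and the only stated limit for bilirubin is the 30% rise, which this patient passes. It narrows the gap without closing it.

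A reader might infer more: that these patients have no bilirubin rule, or that item g is seriously weakened. The documents do not support either. Repeat testing is mandatory, item g is discretionary and needs at least three patients, and the working above gives at most about one affected patient.

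**Conclusion.** The gap is real on the text. Item a has no limb for a non-Gilbert patient with an averaged baseline above 1.00 and up to 1.15 x ULN. The 1.15 bound follows from the documents alone. The consequence is a judged stop in place of a mandatory one, for an isolated rise to 3.0 mg/dL.

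The count of 0.01 to 1.35 patients in 36 rests wholly on assumed distributions and should be read as usually none or one. The chance that such a patient then reaches 3.0 mg/dL in isolation cannot be estimated from the documents and is probably small. No endpoint or analysis is affected. I rate this a minor, optional correction to the wording of a safety rule.

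**What to change.** In 4.4.1 and in the synopsis, reword the first limb of item a to: *TB of 3.0 mg/dL or more in every patient except one whose baseline TB is raised because of known Gilbert's syndrome.* Leave the direct-bilirubin limb unchanged. Every enrollable baseline then falls under exactly one limb, and nothing changes for patients already covered.

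The cost is one sentence in two places. It needs no eligibility change, extra test or visit, and causes no screen failures.

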4.5 HANDLING OF PATIENT WITHDRAWAL

In case of withdrawal of consent, and unless otherwise stated by the patient in the informed consent form, Investigators will be encouraged to get information from the medical care provider, in order to follow the medical status of the patients (especially in cases where the patients have withdrawn their consent after having experienced an adverse event). Investigators will also be expected to try as much as possible to re-contact those patients at the end of the trial, in order to obtain status.

If subject discontinues from the study for any reason, before the End of Treatment Visit, the investigator will make all attempts to carry out all End of treatment Visit procedures.

5 STUDY TREATMENTS / IP MANAGEMENT

Saroglitzazar magnesium 2 mg or Saroglitzazar magnesium 4 mg or placebo tablet will be administered in patients with Primary Biliary Cholangitis once daily in the morning before breakfast without food, for a period of 16 weeks.

5.1 TREATMENTS TO BE COMPARED

5.1.1 Investigational Product Description

The products that will be used in this study are outlined in Table 2.

Table 2 Identity of Study Drugs

Study Drug	Formulation	Strength	Route	Manufacturer
Saroglitazar Magnesium	Tablet	2 mg	Oral	[REDACTED]
Saroglitazar Magnesium	Tablet	4 mg	Oral	[REDACTED]
Placebo	Tablet	Matching placebo	Oral	[REDACTED]

Data source: Investigator's Brochure

A series of horizontal black bars of varying lengths, suggesting a visual representation of data or a signal. The bars are arranged vertically, with some shorter bars at the top and a longer bar near the bottom. The lengths of the bars correspond to the values in the following table.

5.1.2 Comparator Drug Description

Placebo will be used as comparator, which will be formulated as tablets, and will contain above mentioned excipients in section No. 5.1.1. The IP will be manufactured following current-Good Manufacturing Practice (cGMP) guideline.

5.2 DOSAGE AND TREATMENT SCHEDULE

Patients will receive either Saroglitazar magnesium 2 mg or Saroglitazar magnesium 4 mg or placebo orally once each morning before breakfast without food (as determined by the patient's schedule) for 16 weeks during the double-blind treatment period. However, during

Approved by: [name]	Protocol No. SARO.16.004 Version No.: 6.0
----------------------------------	--

scheduled visits patients will have the IP administered on site after the blood sample collection.

5.3 PACKAGING, LABELLING AND RE-SUPPLY

Tablets of Saroglitazar magnesium (2 mg and 4 mg) and placebo will be packed, labeled and supplied by the Sponsor according to all local legal requirements. [REDACTED]

All drug supplies must be stored in a temperature-controlled environment for ambient temperature 20-25°C.

All Investigators will be provided with a sufficient number of units of the IP for the conduct of the study. Investigational product would then be dispensed to each subject in such a way that the subject can take the doses in accordance with the protocol. A drug accountability log for recording the receipt, storage, dispensing and return of the IP will be maintained by the Investigator or any designated personnel.

Site will contact the sponsor/designee for re-supply of the Investigational product.

After the study has been completed, the PI must account for all study drug used, unused and partially used. All study drugs will be destroyed at the site (per site's SOPs) or returned to the Sponsor (or designee). Unused drug supplies will be destroyed at the site after approval

**Zydus Discovery
DMCC**

CLINICAL TRIAL PROTOCOL

Saroglitzaz Magnesium – Phase II

SARO.16.004

CONFIDENTIAL

PAGE 41 OF 82

for the same by the Sponsor. No study drug will be destroyed or returned until drug accountability has been performed by the study monitor.

5.4 STORAGE CONDITIONS

Investigational product will be stored at room temperature (20°C to 25°C) and in dry place, protected from light. If the IP temperature extends outside the 20-25°C range, a temperature excursion must be documented in the study-specific temperature log, and sent to the Sponsor. If the excursion is within 15-30°C, quarantine is not required, and the IP is acceptable for use. If the excursion is outside of the 15-30°C range, the IP must be quarantined until a decision on the stability of the IP is made by the Sponsor. If the excursion goes beyond the range of 15-30°C it will be considered as a protocol deviation. All IP supplies in the study will be stored in a secure place with access limited to the Site Pharmacist or the Investigator designated site staff.

5.5 BLINDING / UNBLINDING

The study is a double blind study, hence study participants and investigator will not be made aware which preparation (Saroglitzaz magnesium 2 mg or Saroglitzaz magnesium 4 mg or placebo), is to be administered. The randomization code will be available to the Investigator, for emergency purposes only. The randomization code will be available on each kit which is concealed in the form of scratchcard. In an emergency, when knowledge of the patient's treatment assignment is essential for the clinical management or welfare of the patient, the investigator should make every effort to first contact the Sponsor/ designee.

The formulation of Saroglitzaz magnesium (2 mg and 4 mg) and placebo IPs will be similar in appearance to make any difference in treatment unobvious to the patients and to maintain adequate blinding of evaluators. Neither the Investigator nor the patient should be able to identify the received treatment.

In an emergency, when knowledge of the patient's treatment assignment is essential for the clinical management or welfare of the patient, the investigator should make every effort to first contact the Sponsor/ designee.

Prior to unblinding the patient's treatment assignment, the investigator should assess the relationship of an adverse event to the administration of the study drug (Yes or No). If the

Approved by:
[name]

Protocol No. SARO.16.004
Version No.: 6.0

blind is broken for any reason, the investigator must record the date and reason for breaking the blind on the appropriate electronic Case Report Form (eCRF) and source documents.

5.6 METHOD OF ASSIGNING PATIENT TO TREATMENT GROUP

Patients will be randomly assigned in 1:1:1 ratio to Saroglitazar magnesium 2 mg, Saroglitazar magnesium 4 mg and placebo. The block randomization schedule will be generated using SAS® software (Version: 9.4 or higher; SAS Institute Inc., USA). Each block will contain investigational medicinal products; Saroglitazar magnesium 2 mg, Saroglitazar magnesium 4 mg and placebo. Each block will contain at least 3 kits of IMP for 3 patients i.e., 1 kit of Saroglitazar magnesium 2 mg, 1 kit of Saroglitazar magnesium 4 mg and 1 kits of placebo.

The subject identification number will be established at the site based on the randomization number/kit number/patient number and will be used to identify the subject throughout the study and will be entered on all documentation. The same subject number will not be assigned to more than 1 subject. If a subject is not eligible to receive treatment, or if a subject discontinues from the study, the same subject number cannot be assigned to another subject.

The subjects will first be screened into the study. Once patients are determined to be eligible, they will be randomized. The subject will also be assigned a study drug in accordance to their assigned treatment group upon completion of the randomization.

Patients will be considered randomized as soon as the first allocation of treatment number is assigned. The first study drug intake should take place as soon as possible after randomization (on the same day), under medical supervision.

5.7 SELECTION OF DOSES

Saroglitazar magnesium 2 mg and 4 mg have favorably modified the lipid profile in the dyslipidemic patients during its development in Phase 2 and 3 studies. Based on the efficacy, safety and tolerability results of Saroglitazar magnesium, it is approved in India at the doses of 2 mg and 4 mg QD for the treatment of “Diabetic Dyslipidemia” and “Hypertriglyceridemia with T2DM not controlled by statin therapy”. Saroglitazar

**Zydus Discovery
DMCC**

CLINICAL TRIAL PROTOCOL

Saroglitazar Magnesium – Phase II

SARO.16.004

CONFIDENTIAL

PAGE 43 OF 82

magnesium 2 mg and 4 mg also demonstrated the favorable effects on ALP and GGT. Hence Saroglitazar magnesium 2 mg and 4 mg doses have been selected for this study.

